#### 9.2 SAMPLE SIZE DETERMINATION

This study is designed to provide a sufficient number of events to build and evaluate a prediction model. The planned sample size of 800 subjects will continue until at least 80 ischemic events have occurred. Under the guideline from Steyerberg of 10 events required per predictor (Steyerberg 2019), this sample size will allow a model with FcγRIIa and up to seven additional predictors to be built. Preliminary results ([name] 2018) suggest that a 4-fold greater incidence of events will be seen in subjects with high platelet expression of FcγRIIa. For

the primary endpoint, there will be at least 95% power to detect a 2-fold greater incidence of cardiovascular endpoints (MI, stroke, and death) with a two-sided  $\alpha < 0.01$  assuming 8% of subjects experience the endpoint. With the planned sample size of 800 a hazard ratio (HR) of 1.9 with a  $p=0.04$  (lower bound of the 95% CI of 1.2) can be detected. For the secondary endpoint, there will be 95% power to detect a hazard ratio of 1.93 when comparing bleeding risk in subjects with high compared with low FcγRIIa expression when assuming a two-sided  $\alpha=0.05$  and 5% of subjects experience bleeding in the low FcγRIIa expression group.

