5.7 Statistical Methods

5.7.1 Analysis of the Primary Objective

The primary analysis of the primary endpoint will be a Cox proportional hazards model. The dependent variable is the number of days from enrolment to the occurrence of a primary endpoint, with censoring at the last day of complete follow-up; independent variables will be FcγRIIa (measured in thousands), age in years, history of diabetes mellitus, prior revascularization, multi-vessel coronary artery disease (MVD) defined as ≥2 vessels or left main with a stenosis ≥50%, chronic kidney disease (CKD) defined as estimated glomerular filtration rate (GFR) < 60 ml/min/1.73 m², prior MI, hypertension, tobacco use, heart failure or LVEF<30%, previous stroke or transient ischemic attack, and peripheral arterial disease. Interest is in the FcγRIIa parameter: point estimate (increase in risk per 1000-unit increase in FcγRIIa), confidence interval and p-value. FcγRIIa will be declared to be associated with cardiovascular risk if the 2-sided p-value from this model is < 0.05.

A set of exploratory/sensitivity and subgroup analyses based on the Cox model will also be conducted.

- Instead of censoring at the last day of complete follow-up, censor at the last day of vital status follow-up
- FcγRIIa as the only covariate in the model
- Separate analyses of each component of the primary endpoint: MI and stroke, both censored at the last day of complete follow-up, and death, censored at the last day of vital status follow-up
- Run the primary model in subgroups defined by age (in decades), sex, history of diabetes and prior revascularization (including all covariates except the subgroup variable in the model)
- Run the primary model with the use of DAPT (any use prior to a primary endpoint), and its interaction with FcγRIIa, as additional covariates

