5.10 Determination of Sample Size

This study is designed to provide a sufficient number of events to build and evaluate a prediction model. The planned sample size of 800 subjects will continue until at least 80 ischemic events have occurred. Under the guideline from Steyerberg of 10 events required per predictor (Steyerberg 2019), this sample size will allow a model with FcγRIIa and up to seven additional predictors to be built. Preliminary results ([name] 2018) suggest that a 4-fold greater incidence of events will be seen in subjects with high platelet expression of FcγRIIa. For the primary endpoint, there will be at least 95% power to detect a 2-fold greater incidence of cardiovascular endpoints (MI, stroke, and death) with a two-sided $\alpha < 0.01$ assuming 8% of subjects experience the endpoint. With the planned sample size of 800 a hazard ratio (HR) of 1.9 with a $p=0.04$ (lower bound of the 95% CI of 1.2) can be detected. For the secondary endpoint, there will be 95% power to detect a hazard ratio of 1.93 when comparing bleeding risk in subjects with high compared with low FcγRIIa expression when assuming a two-sided $\alpha = 0.05$ and 5% of subjects experience bleeding in the low FcγRIIa expression group.

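### The sizing text for the primary endpoint uses two-sided alpha below 0.01 although the test is at 0.05, and its power, HR, p-value and confidence bound do not agree with one another

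*SAP*

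**What the plan says.** **Decision rule.** SAP 5.7.1 fits a Cox model with continuous FcγRIIa (per 1,000 units) and 11 other covariates. FcγRIIa "will be declared to be associated with cardiovascular risk if the 2-sided p-value from this model is < 0.05". Protocol 9.4.2 describes the Cox analysis but gives no threshold. Protocol 9.4.1 leaves the planned analyses to the SAP.

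**Sizing.** SAP 5.10 says "there will be at least 95% power to detect a 2-fold greater incidence of cardiovascular endpoints", "with a two-sided $\alpha < 0.01$ assuming 8% of subjects experience the endpoint". The next sentence says that with 800 subjects "a hazard ratio (HR) of 1.9 with a $p=0.04$ (lower bound of the 95% CI of 1.2) can be detected". Protocol 9.2 carries the same paragraph, including the condition "assuming 8% of subjects experience the endpoint". On events: "The planned sample size of 800 subjects will continue until at least 80 ischemic events have occurred". The bleeding power statement in the same paragraph uses two-sided 0.05.

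Neither document says why the primary endpoint is sized at one level and tested at another. Neither gives the high/low split used for sizing, or says whether the 8% is the overall rate or the rate in one group.

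**The concern.** A power statement should describe the test that will be run. Here the level differs from the decision rule by a factor of five. It is also given as an inequality, whereas a power calculation needs one fixed alpha. The following sentence treats p=0.04 as a detection, which a 0.01 test would not.

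A reader of the protocol alone finds 0.01 as the only level attached to the primary endpoint and finds no decision rule. If the result falls between 0.01 and 0.05, the sponsor will have to explain afterwards why the protocol's figure did not govern. The stated power and detectable effect also cannot be relied on when judging whether a null result is informative.

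**Working it through.** **Inputs from the documents:** N = 800; 8% with the endpoint, so 0.08 × 800 = 64 events; follow-up to at least 80 events; 2-fold effect; alpha 0.01 (sizing) and 0.05 (SAP 5.7.1). **Assumed:** a 1:1 high/low split, because none is given. Using 55% high, the pilot figure in Protocol 2.3, changes the Schoenfeld powers by less than one percentage point.

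**1. The stated power, by Schoenfeld.** Power = Φ(√(d/4) × ln HR − z), with ln 2 = 0.6931, z = 2.576 at 0.01 and z = 1.960 at 0.05.

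- d = 64: 4 × 0.6931 = 2.773. At 0.01: Φ(0.197) = 58%. At 0.05: Φ(0.813) = 79%.
- d = 80: 4.472 × 0.6931 = 3.100. At 0.01: Φ(0.524) = 70%. At 0.05: Φ(1.140) = 87%.

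Events needed for 95% power are 4 × (z + 1.645)² / 0.6931², which gives 149 at 0.01 and 109 at 0.05.

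**2. The stated power, as two proportions with 400 per group,** under each reading of the 8%. Power = Φ((difference − z × pooled SE) / unpooled SE).

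| Reading of 8% | Low vs high | Power at 0.01 | Power at 0.05 |
|---|---|---|---|
| Overall | 5.33% vs 10.67% | 58% | 80% |
| Low group | 8% vs 16% | 82% | 94% |
| High group | 4% vs 8% | 42% | 66% |

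For the low-group row, the pooled SE is √(2 × 0.12 × 0.88 / 400) = 0.02298 and the unpooled SE is 0.02280. At 0.01, (0.08 − 2.576 × 0.02298) / 0.02280 = 0.913, so power is 82%. At 0.05 the ratio is 1.533, so power is 94%. No reading reaches 95% at the stated level.

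**3. The HR 1.9 sentence.** ln 1.9 = 0.6419 and ln 1.2 = 0.1823.

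- From the bound: SE = (0.6419 − 0.1823) / 1.960 = 0.2345; z = 0.6419 / 0.2345 = 2.74; p ≈ 0.006. If 1.2 is rounded from anywhere between 1.15 and 1.25, p lies between 0.012 and 0.003.
- From the p-value: p = 0.04 gives z = 2.054; SE = 0.6419 / 2.054 = 0.3125; lower bound = exp(0.6419 − 1.960 × 0.3125) ≈ 1.03.

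The two figures cannot describe the same estimate, and rounding does not close the gap.

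**4. A consistent set at 80 events, 1:1.** SE = 2/√80 = 0.2236. HR 1.9 gives z = 2.87, p ≈ 0.004 and lower bound exp(0.6419 − 0.4383) ≈ 1.23. The smallest significant HR is exp(1.960 × 0.2236) ≈ 1.55 at 0.05, and exp(2.576 × 0.2236) ≈ 1.78 at 0.01.

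**The case against.** **Only one rule exists.** The strongest reply is that the 0.01 is an input to a power calculation, while SAP 5.7.1 alone says what counts as success. This stands. A reader might infer that the primary test has two levels, so that p=0.03 passes one and fails the other. The documents do not support that: such a result would be declared an association and would breach no stated rule. Sizing at a stricter level than the test does not inflate type I error, and had the figures been right it would have been conservative. Nor can SAP 5.7.1 be called a relaxation of a protocol criterion. The protocol sets none, and its own sizing paragraph contains the p=0.04 sentence.

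**HR 1.9 and alpha 0.01.** With 64 events and a 1:1 split, the smallest significant HR at 0.01 is exp(2.576 × 0.25) ≈ 1.90, which might suggest that a 0.01 test was meant. That match needs 64 events, although follow-up runs to at least 80. At 80 events the cutoff is 1.78 and the match disappears. HR 1.9 at 80 events also gives a bound that rounds to 1.2, with p ≈ 0.004, so p=0.04 may be a slip for 0.004. That is an inference, and the sentence is not reliable evidence for either level.

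**More events may accrue.** The stopping rule also requires 18 months of follow-up for the last subject. With uniform 12-month enrolment (assumed), mean follow-up is at least 18 + 6 = 24 months. At the 10% annual rate in Protocol 4.1 and with no losses, 800 × (1 − 0.9²) ≈ 152 events, and power for HR 2 is about 95.5% at 0.01. This is a fair point about what the study may achieve. It does not rescue the sentence as written, which rests on 8% of subjects having the endpoint, and the plan guarantees only 80 events.

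**Different model.** All these figures describe an unadjusted high/low comparison. They do not give the smallest effect detectable by the adjusted continuous model. This stands, and it applies equally to the plan's own figures.

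**Conclusion.** The point holds as a fault in the sizing text, not in the decision rule. The primary test is at two-sided 0.05. The sizing paragraph uses a different level without explanation, calls detectable a p-value that this level would reject, and pairs that p-value with a bound implying p of about 0.006. Its power of at least 95% is not reached with 64 or 80 events: 58% or 70% at 0.01, and 79% or 87% at 0.05. The most favourable reading of the 8% gives about 82% and 94%.

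The power figures rest on the assumed 1:1 split, on HR 2 between high and low groups, and on the event counts shown. The conflict between p=0.04 and the bound of 1.2 needs only the usual normal approximation on the log-HR scale. The consequence is limited: no false-positive risk is added, but the stated sensitivity of the study is unreliable.

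**What to change.** 1. Keep the SAP 5.7.1 rule. In Protocol 9.2 and SAP 5.10, replace the alpha of below 0.01 for the primary endpoint with two-sided alpha = 0.05.
2. Restate the power at that alpha with the event count and split written out: about 87% for HR 2 with 80 events and a 1:1 high/low split. Say that this describes a high/low comparison and not the adjusted continuous FcγRIIa model, or recompute it for that model. If more than 80 events are relied on, state the number and the annual rate and follow-up behind it.
3. Say what the 8% refers to.
4. Replace the HR 1.9 / p=0.04 / 1.2 sentence with a consistent set. For example, with 80 events at 1:1, HR 1.9 corresponds to p of about 0.004 and a lower bound of about 1.23, and the smallest significant HR at 0.05 is about 1.55.
5. Copy the SAP 5.7.1 decision sentence into Protocol 9.4.2.

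Do this before FcγRIIa is analysed against outcome. Changing the alpha alone is not enough, because the 95% claim would still be wrong at 0.05 with 80 events. The cost is wording and a short recalculation, with no extra subjects or data. The downside is that the stated power becomes less favourable.

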### 7.1 LOST TO FOLLOW-UP

Every effort will be made to minimize the number of subjects who are lost to follow-up. The following actions must be taken if a subject misses a required study visit:

- The site will attempt to contact the subject and reschedule the missed visit and counsel the subject on the importance of maintaining the assigned visit schedule and ascertain if the subject wishes to and/or should continue in the study.
- Before a subject is deemed lost to follow-up, the investigator or designee will make every effort to regain contact with the subject (3 telephone calls and, if necessary, a certified letter to the subject's last known mailing address or local equivalent methods). These contact attempts should be documented in the subject's medical record or study file.
- Should the subject continue to be unreachable, he or she will be considered to have withdrawn from the study with a primary reason of lost to follow-up.
- Electronic medical records may be used to assess vital status (alive or dead) at the end of the study provided the subject has not withdrawn consent for follow-up.

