5.3 Study Subjects

A clear accounting of the disposition of all subjects who enter the study will be provided, and a summary of the number and percentage of subjects by center will be produced.

A subject is considered to have completed the trial if the subject has adequate follow-up to assess all study outcomes through either the final study telephone visit or the date of death. For subjects who did not complete the trial two different dates are of interest: the last date for which information on nonfatal study outcomes is available and, if later, the date the subject died or was last known to be alive. The

latter can differ from the former when public records are used to determine vital status in a subject who is lost to follow-up.

Completeness of follow-up for the primary endpoint can therefore be assessed in multiple ways, and will be tabulated as follows:

1. Percentage of subjects with complete follow-up for all study outcomes through the final study telephone visit or the date of death
2. Percentage of subjects with complete follow-up for primary study outcomes through the final study visit or the occurrence of a primary study outcome,
3. Percentage of subjects with complete follow-up for vital status
4. Mean percentage of potential follow-up for primary study outcomes as defined in 2 above (defined as 100% for a subject with complete follow-up, or 100 times the number of days of complete follow-up divided by the number of days between the subject's Day 1 visit and the end of study for a subject with incomplete follow-up)
 - a. This percentage of follow-up will be subdivided into percentages of follow-up on DAPT and on monotherapy.
5. Mean percentage of potential follow-up for vital status as defined in 3 above (defined as 100% for a subject with complete follow-up or a subject who died, or 100 times the number of days of vital status follow-up divided by the number of days between the subject's Day 1 visit and the end of study for subjects with incomplete follow-up)

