5.6 Objectives and Endpoints

The primary objective of the study is to determine whether platelet expression of FcγRIIa is associated with risk of MI, stroke, and death.

Secondary objectives are:

- Develop a score that combines clinical characteristics plus platelet expression of FcγRIIa to determine the risk of MI, stroke, and death.
- Determine whether platelet expression of FcγRIIa is associated with risk of major bleeding.

The primary endpoint is the composite of death, MI, and stroke. A secondary endpoint is clinically significant bleeding according to BARC type 2-5.

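### The first sensitivity analysis in SAP 5.7.1 counts time after loss to follow-up as free of MI and stroke, although only death can be observed in it

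*SAP*

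**What the plan says.** The composite is defined in SAP 5.6: "The primary endpoint is the composite of death, MI, and stroke". The primary Cox model in SAP 5.7.1 runs from enrolment to the first such event, "with censoring at the last day of complete follow-up". The first item in the list of exploratory and sensitivity analyses then reads: "Instead of censoring at the last day of complete follow-up, censor at the last day of vital status follow-up". It does not limit the change to the death component.

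SAP 5.3 gives each non-completer two dates: "the last date for which information on nonfatal study outcomes is available and, if later, the date the subject died" or was last known alive. It explains that the "latter can differ from the former when public records are used to determine vital status in a subject who is lost to follow-up". Protocol 7.1 shows how far apart they can be: "Electronic medical records may be used to assess vital status (alive or dead) at the end of the study", provided consent for follow-up has not been withdrawn.

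Elsewhere the SAP keeps the two dates apart. The third bullet of the same list analyses the components separately: "MI and stroke, both censored at the last day of complete follow-up, and death, censored at the last day of vital status follow-up". SAP 5.9.1 follows the same division when it imputes a missing event date: last complete follow-up for MI and stroke, last known alive for death.

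Neither document says how an MI or stroke between the two dates would be found or handled.

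**The concern.** Take a subject lost at month 6 and found alive in records at month 30. The first bullet keeps this subject in the composite risk set for a further 24 months. In that time a death would count, but an MI or stroke would not be seen, so the model treats unascertained time as observed freedom from MI and stroke.

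This is the only listed check on how the composite result depends on the censoring rule. If it departs from the primary analysis, the reader will want to know whether the primary result is sensitive to loss or the check is distorted by its own construction. If the two agree, the same doubt applies. As written, the SAP gives no way to tell.

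**Working it through.** The documents state no figure for this rule and no loss rate, so there is no plan figure to reproduce. The size below is an illustration.

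**Inputs from the documents.** Composite event rate 10% per year; about 12 months of accrual and at least 18 months of follow-up after the last enrolment, so 1.5 to 2.5 years per subject (Protocol 4.1, 4.2); 55% with high FcγRIIa (Protocol 2.3); hazard ratio 2 as the design effect (SAP 5.10, a 2-fold incidence).

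**Assumed inputs.** Loss of 3–15% per year, by FcγRIIa group; deaths 30–50% of first events; vital status recovered to study end for all lost subjects; FcγRIIa as high/low; exponential event and loss times.

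**Formula.** Let *d* be the share of the composite hazard due to death and *L(t)* the share of a group's risk set that is in the gap at time *t*. A subject in the gap can contribute only the death part, so the group's apparent hazard is its true hazard × [1 − (1 − *d*) *L(t)*]. With a common effect on all components:

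apparent HR ≈ true HR × [1 − (1 − *d*) *L*high] / [1 − (1 − *d*) *L*low]

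The ratio is 1 when loss is equal in the two groups.

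**Numbers at one year, *d* = 0.4.** Loss 5% per year (low FcγRIIa) against 15% (high): *L*low = 1 − exp(−0.05) = 0.0488 and *L*high = 1 − exp(−0.15) = 0.1393. The factor is (1 − 0.6 × 0.1393)/(1 − 0.6 × 0.0488) = 0.9164/0.9707 = 0.944, so a true 2.0 reads about 1.89. The other rows follow in the same way. Large-sample simulation (1.0–1.5 million subjects per scenario, death share 30–50%) agrees:

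| Assumed loss per year, low / high FcγRIIa | Factor from formula | Simulated HR, true 1.0 | Simulated HR, true 2.0 |
|---|---|---|---|
| 3% / 6% | 0.982 | shift about 2% | shift about 2% |
| 3% / 10% | 0.960 | 0.95–0.96 | 1.90–1.94 |
| 5% / 15% | 0.944 | 0.93–0.95 | 1.85–1.91 |
| 15% / 5% | 1.059 | 1.05–1.08 | 2.11–2.15 |

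With loss independent of outcome given FcγRIIa, censoring at complete follow-up returned 1.00 and 2.00–2.02.

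**When there is no shift.** Equal loss with a common effect: 1.00 and 1.99–2.00. Loss acting only through a covariate in the model: 0.996 and 1.99.

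**Component-specific effects.** With equal loss, MI/stroke hazard ratio 2 and death hazard ratio 1, the vital-status rule gives 1.57 where the truth is 1.60.

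**Rate.** With equal loss the crude composite rate is understated by about 3–7%. With about 14% lost, per 800 subjects the rule gains about 5 deaths and leaves about 7 first MIs or strokes unseen while the subject stays at risk.

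**At N = 800** (4,000 simulated trials, death share 40%, loss 5% / 15%): with no true effect, p < 0.05 in 6.7% of trials against 4.8% under the primary rule; at a true hazard ratio of 1.7, 75% against 84%. With loss reversed: 6.8% against 4.4%, and 91% against 82%.

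**The case against.** Four arguments count on the other side.

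*The obvious route to bias is already adjusted for.* Protocol 9.4.2 links higher FcγRIIa to older age, diabetes and prior revascularization, and a reader might infer that loss therefore differs by FcγRIIa and biases this check. All three are covariates in the SAP 5.7.1 model, which the bullet leaves unchanged, and loss acting through an adjusted covariate did not move the hazard ratio. This stands. Bias needs loss tied to FcγRIIa beyond the covariates, or effects that differ by component, and the documents give no evidence of either.

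*The bullet has a proper purpose.* It brings in deaths found only in records, which the primary rule drops. Suppose 10% of deaths in low and 30% in high FcγRIIa subjects are found only that way, with complete follow-up ending at the last 6-monthly call. The primary rule then gives about 0.89–0.92 for a true 1.0 and 1.78–1.85 for a true 2.0, while the bullet gives about 1.00 and 1.99–2.02. This also stands: which rule is nearer the truth depends on the loss mechanism, so calling the bullet biased by construction would go too far. Where loss depends on both frailty and FcγRIIa, both rules are off and the bullet more so (true 1.88: primary 1.80, bullet 1.76). The stacked model proposed below was close to the truth in the differential-loss and record-only-death scenarios alike.

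*The effect is small and the loss rates are assumed.* Protocol 7.1 sets out active contact procedures, and records may be used but need not be. Full recovery of vital status is therefore an upper limit.

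*Other outputs help.* The third bullet separates the components, and the completeness tables in SAP 5.3 would show how much time lies in the gap. Neither gives a composite estimate with the right dates. The understated rate matters less, since SAP 5.7.1 puts the interest in the FcγRIIa coefficient.

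**Conclusion.** The point holds as a minor defect of specification. The first sensitivity bullet treats gap time as MI- and stroke-free when the SAP's own definitions say that those outcomes are unknown there. The composite rate is understated wherever gaps exist. The hazard ratio shifts by about 2–8% in either direction under the assumed differential loss of 3–15% per year with full recovery of vital status. The shift is nil when loss is unrelated to FcγRIIa and the effect is common to all components, or when loss acts only through adjusted covariates. The true size is unknown because no loss rate is stated.

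A reader might infer that the primary result is compromised. It is not: the declaration rule in SAP 5.7.1 uses only the primary model, and this analysis is labelled exploratory/sensitivity. Nor do the documents support an expectation of heavy, strongly FcγRIIa-dependent loss, from which larger distortions could be calculated.

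**What to change.** Replace the first bullet with one composite analysis that uses the third bullet's dates:

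- Give each subject two rows in a Cox model stratified by event type, one for MI/stroke and one for death.
- Censor the MI/stroke row at the last day of complete follow-up and the death row at the last day of vital status.
- End both rows at the first observed event.
- Fit one common FcγRIIa coefficient with the primary covariates and a robust variance clustered on subject.

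This keeps the deaths found only in records and adds no unobserved MI- and stroke-free time. In simulation it gave 1.98–2.03 for a true 2.0 and 0.99–1.00 for a true 1.0 across the differential-loss scenarios.

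The cost is SAP wording and a few lines of R, with no new data. The downside is the assumption of a common FcγRIIa effect on fatal and non-fatal events, which the third bullet lets the reader check. Inverse-probability-of-censoring weights on the primary model would be a reasonable extra for loss explained by measured covariates, but are optional. If the bullet is kept as it stands, the SAP should at least state that gap time is assumed free of MI and stroke.

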The primary endpoint will be the composite of death, MI, and stroke. MI will be defined in accordance with the 4th universal definition (Thygesen 2018) and stroke consistent with consensus guidelines (Sacco 2013). The incidence of clinically significant bleeding will be determined using the Bleeding Academic Research Consortium (BARC) scale (Mehran 2011) and is defined as BARC type 2-5. Study endpoint events will be confirmed by the review of medical records by the investigator and all relevant medical records will be obtained by the site for submission to the sponsor (as described in Section 10.8). Subjects who experience an endpoint event will continue to be followed throughout the entire study and any subsequent endpoint events will also be confirmed and recorded. See Appendix 1 for study endpoint event definitions.

A total of approximately 800 subjects will be enrolled at approximately 10-20 sites in the US. It is anticipated that it will take about 12 months to enroll the total number of subjects. The study and subject follow-up will continue until 1) at least 80 ischemic events (MI, stroke, and death) have occurred, and 2) the last subject enrolled has completed at least 18 months of follow-up. Based on an annual ischemic event rate of 10%, the overall length of participation in the study is anticipated to be up to 3 years. Results will be monitored during the course of the study.

Figure 5 Schematic Overview of the Study

MI=myocardial infarction; NSTEMI= non-ST-segment elevation MI, STEMI= ST-segment elevation MI

\* Subjects who experience an endpoint event will continue to be followed throughout the entire study and any subsequent events will also be confirmed and recorded.

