#### 4.2 END OF STUDY DEFINITION

The study will be stopped when 1) at least 80 ischemic events (MI, stroke, and death) have been confirmed and 2) the last subject enrolled has completed at least 18 months of follow-up. The study will be considered complete once all subjects have had their last telephone visit.

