#### 9.4.2 ANALYSIS OF THE PRIMARY OBJECTIVE

Cox proportional hazards models will be fit to compare the risk of the primary endpoint based on platelet expression of FcγRIIa as a continuous variable. Subjects will be followed until their earliest MI, stroke, or death. Patients who do not experience the composite endpoint will be censored at their last telephone follow-up. Time to the primary endpoint will be calculated as days from study enrollment. Models will be adjusted for potential confounders including sex and other subject demographics and medical history collected at baseline. In the pilot study, it was observed that older age, diabetes mellitus, and prior revascularization were associated with higher platelet FcγRIIa expression.

A set of sensitivity analyses will evaluate FcγRIIa as a binary endpoint, which each analysis using a different threshold for classifying FcγRIIa as high or low. In particular, these analyses will explore whether a binary or a continuous measure of FcγRIIa provides greater predictive value, and whether or not a threshold of  $\geq 11,000/\text{platelet}$  is optimal.

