#### 9.4.6 SUB-GROUP ANALYSES

Not applicable.

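### SAP 5.7.1 refits the primary Cox model in each age decade on too few events and plans no FcγRIIa interaction for age, sex, diabetes or prior revascularization; use full-cohort interaction models instead

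*SAP*

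**What the plan says.** The primary model in SAP 5.7.1 has 12 variables: FcγRIIa, age in years, diabetes, prior revascularization, multi-vessel disease, chronic kidney disease, prior MI, hypertension, tobacco use, heart failure or low LVEF, prior stroke or TIA, and peripheral arterial disease. Sex is not among them, although Protocol 9.4.2 names it as an adjustment variable.

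Under exploratory, sensitivity and subgroup analyses, the SAP then asks the statistician to "Run the primary model in subgroups defined by age (in decades), sex, history of diabetes and prior revascularization", keeping every covariate except the one that defines the subgroup. It also plans "Separate analyses of each component of the primary endpoint: MI and stroke, both censored at the last day of complete follow-up", plus death, without stating which covariates those models carry. The only interaction listed is FcγRIIa by DAPT use. There is no minimum event count, no rule for pooling age bands, and no reduced or penalised model.

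Protocol 9.4.6, on subgroup analyses, reads "Not applicable". Protocol 9.4.2 reports from the pilot that "older age, diabetes mellitus, and prior revascularization were associated with higher platelet FcγRIIa expression".

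**The concern.** Splitting the cohort by decade divides a modest number of events into small parts, while the model stays almost as large as in the full cohort. In a small part, a covariate with no events at one level has no finite coefficient, and the FcγRIIa estimate becomes imprecise or fails.

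Separate fits also do not answer the question that a subgroup analysis is meant to answer, which is whether the FcγRIIa effect differs by age, sex, diabetes or revascularization history. Without an interaction estimate, readers will set a significant decade beside a non-significant one and infer a difference. This matters here because the stated aim is a precision-medicine tool, and because three of the four factors were linked to FcγRIIa in the pilot.

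**Working it through.** **The plan's own figure.** SAP 5.10: "The planned sample size of 800 subjects will continue until at least 80 ischemic events have occurred". At 10 events per predictor, 80 / 10 = 8 predictors, which matches the stated FcγRIIa plus seven.

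**Expected events.** Protocol 4.1 plans for about 800 subjects, accrued over roughly 12 months, with an annual event rate of 10%. Protocol 4.2 also requires that "the last subject enrolled has completed at least 18 months of follow-up". Both stopping conditions must be met, so 80 is a floor. With uniform accrual, follow-up runs from 1.5 to 2.5 years. With constant hazard λ, expected events = 800 × [1 − (e^(−1.5λ) − e^(−2.5λ)) / λ].
- λ = 0.10: 800 × (1 − 0.8191) ≈ 145
- λ = −ln(0.9) = 0.1054: 800 × (1 − 0.8104) ≈ 152
- λ = 0.097 (registry rate in Protocol 2.3): 800 × (1 − 0.8240) ≈ 141

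An assumed 5% yearly loss to follow-up lowers the 141–152 range to 134–144.

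**What the rule would need, with no assumed age split.** Counting each variable as one term:
- Age decade: 12 − 1 = 11 terms, so 110 events in that decade. This is impossible at 80 events. At 152 it needs 110 / 152 = 72% of all events in one decade.
- Diabetes or prior revascularization, both levels: 2 × 110 = 220 events.
- Sex, both levels: there is no sex term to drop, so 2 × 120 = 240 events.

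**Illustrative decades.** The documents give no age distribution. The shares below are assumed and applied to 80 and 145 events.

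| Decade | Assumed share | Events | Events per term (11) |
|---|---|---|---|
| under 50 | 5% | 4–7 | 0.4–0.7 |
| 50s | 15% | 12–22 | 1.1–2.0 |
| 60s | 35% | 28–51 | 2.5–4.6 |
| 70s | 30% | 24–44 | 2.2–4.0 |
| 80 and over | 15% | 12–22 | 1.1–2.0 |

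A two-level subgroup holding 30–70% of events has 2.0–5.1 events per term at 80 events (24/12 to 56/11) and 3.6–9.2 at 145 (43.5/12 to 101.5/11).

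**What happens to the fits.** These are simulated Cox fits with assumed covariate prevalences.
- *Nuisance covariates* (1,200 fits per scenario): at least one infinite coefficient in 94% of fits at 4 events, 75% at 7, 43% at 12, 10% at 22 and 4% at 28.
- *FcγRIIa itself* (200 fits per scenario, true HR 1.4 per SD, log HR 0.34): absolute log HR above 3 in 60% of fits at 4 events, 2.5% at 7 and none at 12.
- *FcγRIIa at 8–16 events in a band* (300 fits per scenario): median log HR 0.39–0.43, SD 0.34–0.81, coverage 92–94%. An SD of 0.34 puts the 95% limits a factor of e^(1.96×0.34) ≈ 1.9 either side of the estimate; an SD of 0.81 gives e^(1.96×0.81) ≈ 4.9.

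**Why comparing decades misleads.** With FcγRIIa split 50/50 and true HR 2, power within a band of D events is Φ(½√D × ln 2 − 1.96): 16% at D = 8 and 45% at D = 28. If both bands truly have HR 2, the chance that exactly one is significant is 0.45 × 0.84 + 0.55 × 0.16 ≈ 47%.

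**The interaction alternative.** For a two-level factor with event share s, the variance of the log ratio of HRs is 4/(Ds) + 4/(D(1−s)). For a ratio of 2:
- D = 80: power 30% (s = 0.3) to 34% (s = 0.5)
- D = 140: power 47% to 54%

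In 700 simulated cohorts of 800 with about 84 events, FcγRIIa-by-age and FcγRIIa-by-diabetes interactions were estimable in all but 1 of 1,400 fits, with type I error 4.4–5.7%.

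**Stroke alone.** If stroke is an assumed 10–20% of events, there are 8–16 events at the floor and about 15–29 at 145. With 12 terms that is 0.7–1.3 and 1.2–2.4 events per term.

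**The case against.** The strongest reply is that the SAP's interest is in the FcγRIIa coefficient, and an infinite nuisance coefficient does not by itself spoil it. That largely stands. From about 8 events upward, simulated coverage for FcγRIIa was 91–98%. Stroke-like fits with 10 and 15 events gave a median log HR of 0.35 and coverage of 95.5% and 96.5%. The usual problem is imprecision, with some upward bias in small bands; outright failure is confined to the sparsest.

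Several other points also stand. The analyses are exploratory and carry no decision rule. The 10-per-predictor rule was stated for the prediction model; it is used here only as the plan's own yardstick. An interaction model with 13 terms also misses it at the floor (80 / 13 = 6.2), although not at 145 events (11.2). Protocol 9.4.1 defers the planned analyses to the SAP, so the conflict with 9.4.6 is minor.

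A reader might go further and infer three things that the documents do not support:
- *That these results are unusable in general.* This is shown only for the sparsest decade, whose size is assumed.
- *That no subgroup difference can be tested.* None is planned for these four factors, but a full-cohort interaction can be fitted, and the SAP already plans one for DAPT.
- *That the MI analysis fails.* If MI is 40–50% of events, it has 32 or more even at the floor. Simulated fits were stable at 40 and 56 events.

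Full adjustment of the component analyses is also an inference, since the SAP states their censoring but not their covariates.

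**Conclusion.** The concern holds for the age-decade refits and for the missing interaction tests. No decade can meet the SAP's own events-per-predictor figure at 80 events, and at 152 one would need 72% of all events. The sparsest decade, at about 4–7 events, may yield no estimable FcγRIIa effect, and the remaining decades will be imprecise. The two-level subgroups are thin but not shown to break down; their weakness is that separate fits provide no estimate of the difference.

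The primary conclusion is unaffected. The shortfall against the rule follows from the documents' figures. The decade counts, stroke share and simulated failure rates rest on stated assumptions. Omitting age in years within a decade may let back some age confounding; its size has not been estimated, so it is secondary. Overall this is an inexpensive improvement to exploratory analyses.

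**What to change.** In SAP 5.7.1, replace the separate subgroup fits with one full-cohort model per factor: the primary model plus an FcγRIIa-by-factor interaction for age (continuous), sex, diabetes and prior revascularization. Add a sex main effect in the sex model. Report the interaction estimate with its 95% CI and the FcγRIIa HR at stated factor levels. Label the results exploratory and state the low power, about 30–54% for a two-fold ratio of HRs between two-level groups.

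State the covariates for the component analyses. If the full set is intended for stroke, use a reduced or Firth-penalised model instead, for example one clinical linear predictor in place of the separate covariates.

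Reconcile Protocol 9.4.6 with the SAP.

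The cost is SAP wording, a short protocol correction and slightly different code, with no new data. The downside is that covariate effects are assumed common across subgroups.
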